6.5 Staffing of the Facility

The facility will be staffed by research team members who will be present in the facility 8 am through 5 pm each day (including weekends). An on-call physician will be available for all hours, including evenings and weekends, for the management of illness or to address any questions or concerns from any study participants. The on-call physician can make decisions on the treatment of influenza, use of supportive care, and escalation of care. For overnight hours, a thermometer and over the counter antipyretics will be made available. Participants will be able to request video or phone call contact with the covering physician to discuss any concerns. The on-call physician will use their judgement whether they may need to report into the quarantine research unit to directly assess the participant.

6.6 Treatment of Influenza

For the healthy young adult, influenza infection is largely a self-limiting viral infection which only requires rest and supportive care. No later than 72 hours of a Recipient demonstrating any criteria which satisfy the primary outcome of SAR influenza infection and immediately upon onset of fever $>102^{\circ}\text{F}$, meeting other criteria for a grade 3 adverse event (see Appendix A), or as required by the clinical judgement of study physicians, therapeutic intervention with an approved influenza antiviral agent (i.e., oseltamivir or baloxavir marboxil) will commence. Meanwhile, the subject will be requested to provide exhaled breath specimens; the subject will not be required to participate in additional *exposure event* group activities.

Recipients that become secondarily influenza infected may provide voluntary consent to continue in the CHIVITT as a Donor; the Donor consent form must be reviewed and signed in order for the participant to

continue as a Donor. Under this circumstance, treatment with the influenza antiviral agent will be withheld and the subject (now considered an infectious subject) will be instructed to participate in *exposure event* group activities, as a Donor participant. The participant may choose to terminate their participation as a Donor participant at any time before the maximum 5 days, as originally intended for a Donor participant. Upon deciding to terminate in participation in the CHIVITT, the subject can be administered an influenza antiviral agent and may be discharged. Under all circumstances, symptoms of an influenza infection are intended to be followed to resolution and this may be done through phone call contacts upon discharge; the dates of resolution of influenza symptoms are intended to be documented.

6.7 Supportive Care

The management of illness by the study physicians will allow for the use of supportive care measures. The study physician may treat the subject with symptom-directed, over-the-counter therapies, such as non-steroidal anti-inflammatory drugs (NSAIDs), acetaminophen, decongestants, or antihistamines. Oral hydration (oral fluids) may be provided, should a subject become dehydrated due to poor appetite. Humidification of room air may also be performed to improve the comfort of the participant. Nonetheless, support care is intended to be limited for subjects that do not demonstrate any illness criteria that may satisfy conditions requiring escalation of care.

6.8 Escalation of Care

In rare instances a subject's illness may meet criteria for escalation of care, wherein more in-depth evaluation and/or treatment of illness may be necessary. Escalation of care may involve referral to the local Emergency Room or Urgent Care Center, as the investigator has deemed the severity of illness to be beyond the simple supportive care which can be provided by the EMIT-2 facility. Subjects infected with influenza will be monitored for the possible development of severe symptoms and any influenza complications (as outlined in [section 2.5.1](#)). If a subject has a severe influenza complication(s) or has shortness of breath with an $\text{SpO}_2 < 89\%$ or has any 2 severe grade vital signs (see [Appendix A](#) for severity grading for vital signs), then escalation of care is to be considered.

Therapeutic intervention with an approved influenza antiviral agent (oseltamivir or baloxavir marboxil) should commence immediately upon recognition that escalation of care for influenza is necessary and if not yet already initiated. Study physicians have the authority to exercise clinical judgement to initiate referral for pulmonary function testing, chest radiography, institution of supplemental oxygen, or the initiation of bronchodilators for management. Escalation of care may also include immediate referral to the local urgent care or emergency department for rapid diagnostic testing and/or management. The intent is that there will be no delay in providing appropriate escalation of care to study participants and that the study physicians document their decision-making process. UMB and/or its affiliated institutions or healthcare groups will not provide financial compensation or reimbursement for the cost of referred care that may be provided. The institution or group providing medical treatment will charge the participant's insurance carrier.

Meanwhile, the ill subject will not be required to participate in *exposure event* group activities and will be afforded the time to rest and recover or be referred for higher-level care. Participant preference is intended to be honored. However, when the investigator judges that escalation of care is necessary for the welfare of the participant then participation in *exposure event* activities will be prohibited.

6.9 Discharge Criteria

Subject discharge is planned at approximately 14 days (for Recipient participants) or 2-5 days (for Donor participants) after entry. To be eligible for discharge home, the participant must meet the following criteria: no greater than moderate severity influenza signs or symptoms (Appendix A) and are clinically stable during their stay. In addition, the participant must attest that they feel well enough to provide their own self-care. Otherwise, Recipients will be discharged as described in escalation of care (Section 6.8). Recipients must be at least 2 days post the end of their last exposure event to be eligible for discharge. We may discharge Recipients with a home influenza test to ensure that we do not miss late onset, long latency, influenza infection. However, recipients who have contracted the flu but do not wish to be a donor may be discharged earlier. In this case, they must meet the discharge criteria described above for discharge home. All other instances will be handled as described in Section 6.8.

6.10 Subject Withdrawal

Subjects may voluntarily withdraw their consent for participation at any time and for any reason, without penalty or loss of benefits to which they are otherwise entitled. The PI or appropriate co-investigator may also withdraw a subject for any reason. Withdrawal requests may be temporary (e.g., a single CHIVITT cohort) or permanent.

A subject may withdraw or be withdrawn from this study for any of the following reasons:

- Medical disease or condition, or any new clinical finding for which continued participation, in the opinion of the PI or appropriate co-investigator, would compromise the safety of the subject, or would interfere with the subject's successful participation in CHIVITT
- Subject withdrawal of consent.
- Subject found to have SARS-CoV-2 or other respiratory virus infection.
- Termination of this protocol.
- As deemed necessary by the PI or appropriate co-investigator for noncompliance or other reasons.

6.11 Oversight of Safety and Sponsor-Required Reporting

A monthly safety review will be conducted throughout the CHIVITT periods of the study. The safety review members will consist of the principal investigator, the DMID Medical Officer (MO), Medical Monitor (MM), and Clinical Project Manager (CPM). The information to be reviewed will consist of the following

- Enrollment
- Unsolicited, Non-Serious, Severe or Potentially Life-Threatening Adverse Events or Grade 3+ Adverse Events
- Severe Solicited Influenza Symptoms
- Grade 3 + Abnormal Clinical Laboratory Results Related to Influenza
- SAEs Related to Influenza
- Unanticipated Problems related to trial participation

These listings will include summaries if needed and will be presented as unblinded data from UMD. The reviews may be conducted by email or conference call. Whereupon any safety concerns are potentially detected, a temporary halt may be declared, based on the PI's judgment in consultation with the DMID MM.

The PI should discuss safety events with DMID on an ad hoc basis if deemed by the PI to be of significant concern. Telephone ad hoc meetings will be scheduled as needed to include DMID MO, MM, CPM, and UMD PIs.

Any Unanticipated Problems related to trial participation are to be reported to DMID at the time of IRB reporting. UPs should be submitted to DMID as narratives or a copy of the IRB report for review by MO, MM, and CPM monthly by email to the CPM.

7 SAFETY AND OTHER ASSESSMENTS

7.1 Procedures to be Followed in the Event of Abnormal Laboratory Test Values or Abnormal Clinical Findings

The site PI or designated clinician licensed to make medical diagnoses will record, assess, and follow abnormal laboratory test values and abnormal clinical findings to collect adverse events (AEs) that are observed or reported during the study.

Signs, symptoms, and laboratory findings that are part of mild to moderate influenza disease, including mild or moderate fever and lymphopenia from the time of onset of illness through 7 days post-onset, will not be considered AEs. These signs, symptoms, and laboratory findings (mild and moderate) include the following: runny nose, stuffy nose, sneezing, sore throat, headache, cough, malaise (tiredness), body aches, chills, feverish, shortness of breath, earache, fever, and lymphopenia. Mild to moderate fever and mild to moderate lymphopenia is defined in Appendix A. Influenza infection-related symptoms that are deemed by the investigator to be severe, in addition to severe fever and severe lymphopenia as defined in Appendix A, will be considered as AEs.

Safety will be assessed by the frequency and severity of:

- Study intervention-related serious adverse events occurring from the time of the first exposure event until 2 months post-discharge from the hotel quarantine facility).
- Clinical safety laboratory adverse events occurring from the time of the first exposure event through discharge from the hotel quarantine facility. Parameters to be evaluated include white blood cells (WBCs), absolute lymphocyte count, hemoglobin, platelets, alanine transaminase (ALT), and creatinine (Cr).
- Adverse Events – non-serious adverse events occurring from the time of the first exposure through approximately 28 days post-last-exposure. See below for how adverse events are defined.

7.2 Adverse Events and Serious Adverse Events

Definition of Adverse Events (AE)

ICH E6 defines an AE as any untoward medical occurrence in a patient or clinical investigation subject administered a pharmaceutical intervention regardless of its causal relationship to the study treatment. FDA defines an AE as any untoward medical occurrence associated with the use of a drug in humans, whether or not considered drug-related (21 CFR 312.32 (a)).

An AE can therefore be any unfavorable and unintended sign (including an abnormal laboratory finding), symptom, or disease temporally associated with the use of medicinal (investigational) intervention. The

occurrence of an AE may come to the attention of study personnel during study visits and interviews of a study recipient presenting for medical care, or upon review by a study monitor.

In this study, solicited symptoms of symptomatic influenza infection will be collected from the time of first exposure event through 7 days post-last-exposure and will **not** be considered adverse events. Objective clinical examination findings consistent with the solicited symptom, such as oropharyngeal erythema or lymphadenopathy, will also **not** be considered AEs. Any influenza signs, symptoms or lab findings determined by the clinician to have exceeded the expected severity or any moderate or severe complications, as listed in [Section 2.5.1](#), will be considered unsolicited adverse events and captured on the appropriate data collection form and electronic case report form (eCRF). Events that are not consistent with illness due to influenza will be considered unsolicited AEs as well. Events that occur after administration of antivirals will also be considered unsolicited AEs. Any chronic or stable medical condition that is present at the time that the subject is screened will be considered as baseline and not reported as an AE. However, if the severity of any pre-existing medical condition increases, it should be recorded as an AE.

Classification of an Adverse Event

The determination of seriousness, severity, and causality will be made by an on-site investigator who is qualified (licensed) to diagnose AE information, provide a medical evaluation of AEs, and classify AEs based upon medical judgment. This includes but is not limited to physicians, physician assistants, and nurse practitioners.

Definition of Serious Adverse Events

An adverse event or suspected adverse reaction is considered "serious" if, in the view of either the investigator or sponsor, it results in any of the following outcomes (21 CFR 312.32 (a)):

- death
- a life-threatening adverse event
- inpatient hospitalization or prolongation of existing hospitalization
- a persistent or significant incapacity or substantial disruption of the ability to conduct normal life functions, or
- a congenital anomaly/birth defect.

Important medical events that may not result in death, be life-threatening or require hospitalization may be considered serious when, based upon appropriate medical judgment, they may jeopardize the patient or subject and may require medical or surgical intervention to prevent one of the outcomes listed in this definition. Examples of such medical events include allergic bronchospasm requiring intensive treatment in an emergency room or at home, convulsions that do not result in inpatient hospitalization, etc.

SAEs will be:

- Assessed for severity and relationship to study intervention and alternate etiology (if not related to study intervention) only by the site Principal Investigator or Co-investigator with the training and authority to make a diagnosis.
- Recorded on the appropriate SAE data collection form and eCRF.
- Followed through resolution by a licensed study clinician.
- Reviewed and evaluated by the principal investigator, the DMID MO, MM, CPM, and the IRB/IEC.

Severity of Event

All AEs or SAEs will be assessed for severity according to the toxicity grading scales in [Appendix A](#).

For adverse events (AEs) not included in the protocol-defined grading system, the following guidelines will be used to describe severity.

- **Mild (Grade 1)**: Events that are usually transient and may require only minimal or no treatment or therapeutic intervention and generally do not interfere with the subject's usual activities of daily living.
- **Moderate (Grade 2)**: Events that are usually alleviated with additional specific therapeutic intervention. The event interferes with usual activities of daily living, causing discomfort but poses no significant or permanent risk of harm to the research participant.
- **Severe (Grade 3)**: Events interrupt usual activities of daily living, or significantly affect clinical status, or may require intensive therapeutic intervention. Severe events are usually incapacitating.

AEs characterized as intermittent require documentation of onset and duration of each episode. The start and stop date of each reported AE will be recorded on the appropriate data collection form and eCRF. Changes in the severity of an AE will be documented to allow an assessment of the duration of the event at each level of intensity.

Relationship to Study Intervention

The licensed study clinician's assessment of an AE's relationship to study intervention is part of the documentation process, but it is not a factor in determining what is or is not reported in this study. If there is any doubt as to whether a clinical observation is an AE, the event should be reported. The relationship to study intervention must be assessed for AEs using the terms: related or not related.

- **Related** – The AE is known to occur with the study intervention, there is a reasonable possibility that the study intervention caused the AE, or there is a temporal relationship between the study intervention and event. Reasonable possibility means that there is evidence to suggest a causal relationship between the study intervention and the AE.
- **Not Related** – There is not a reasonable possibility that the administration of the study intervention caused the event, there is no temporal relationship between the study intervention and event onset, or an alternate etiology has been established.

Time Period and Frequency for Event Assessment and Follow-Up

In this study, solicited symptoms of influenza infection will be collected from the time of first exposure event through 7 days post-last-exposure and will **not** be considered adverse events. Unsolicited AEs will be captured starting at the time of exposure through 28 days post-exposure. AEs will be followed through resolution. Resolution of an AE is defined as the return to pretreatment status or stabilization of the condition with the expectation that it will remain chronic.

Adverse Event Reporting

Investigators Reporting of AEs

Information on all AEs should be recorded on the eCRF. Information to be collected for AEs includes event description, date of onset, assessment of severity, relationship to study intervention and alternate

etiology (assessed only the site Principal Investigator or Co-investigator with the training and authority to make a diagnosis), date of resolution, seriousness, and outcome. AEs occurring during the study will be documented appropriately regardless of relationship.

All clearly related signs, symptoms, and results of diagnostic procedures performed because of an AE should be grouped together and recorded as a single diagnosis. If the AE is a laboratory abnormality that is part of a clinical condition or syndrome, it should be recorded as the syndrome or diagnosis rather than the individual laboratory abnormality. Each AE will also be described in terms of duration (start and stop date), severity, association with the study intervention, action(s) taken, and outcome.

Serious Adverse Event Reporting

Investigators Reporting of SAEs

Any AE that meets a protocol-defined serious criterion must be submitted immediately (within 24 hours of site awareness) on an SAE form to the PI ([name]), at the following address: [contact]. Any SAEs that satisfy a reportable new information, according to the UMB IRB, will be reported to the UMB IRB.

In addition to the SAE form, select SAE data fields must also be entered into the DCC system. Please see the protocol-specific MOP for details regarding this procedure.

The DMID Medical Monitor will review and assess the SAE for regulatory reporting and potential impact on study subject safety and protocol conduct.

At any time after completion of the study, if the site principal investigator or appropriate co-investigator becomes aware of an SAE that is suspected to be related to study intervention, the site principal investigator or appropriate co-investigator will report the event to the UMB IRB.

Unanticipated Problems

Definition of Unanticipated Problems (UP)

The Department of Health and Human Services Office for Human Research Protections (OHRP) considers unanticipated problems involving risks to participants or others to include, in general, any incident, experience, or outcome that meets all of the following criteria:

- Unexpected in terms of nature, severity, or frequency given (a) the research procedures that are described in the protocol-related documents, such as the Institutional Review Board (IRB)-approved research protocol and informed consent document; and (b) the characteristics of the participant population being studied;
- Related or possibly related to participation in the research (“possibly related” means there is a reasonable possibility that the incident, experience, or outcome may have been caused by the procedures involved in the research); and
- Suggests that the research places participants or others at a greater risk of harm (including physical, psychological, economic, or social harm) than was previously known or recognized.

Unanticipated Problem Reporting

The investigator will report unanticipated problems (UPs) to DMID, the reviewing Institutional Review Board (IRB) and to the Statistical and Data Management Coordinating Center (SDMCC)/study Sponsor and the lead principal investigator (PI). The UP report will include the following information:

- Protocol identifying information: protocol title and number, PI's name, and the IRB project number;

- A detailed description of the event, incident, experience, or outcome;
- An explanation of the basis for determining that the event, incident, experience, or outcome represents an UP;
- A description of any changes to the protocol or other corrective actions that have been taken or are proposed in response to the UP.

To satisfy the requirement for prompt reporting, UPs will be reported using the following timeline:

- UPs that are serious adverse events (SAEs) will be reported to the IRB and as per reportable new information definition. for Serious Adverse Event Reporting within 24 hours of the investigator becoming aware of the event.
- Any other UP which satisfies one of the categories of a Reportable New Information (RNI) event will be reported to the IRB within five days of the investigator becoming aware of the problem.

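### Sections 7.1 and 7.2 give three conflicting rules on whether mild or moderate influenza illness is an adverse event, so its classification depends partly on antiviral timing and role

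*Protocol*

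**What the plan says.** Three rules apply to the same mild or moderate influenza finding.

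- **Onset rule (Section 7.1).** Listed signs, symptoms and laboratory findings of mild to moderate influenza, lymphopenia included, "from the time of onset of illness through 7 days post-onset, will not be considered AEs".
- **Last-exposure rule (Section 7.2, Definition of Adverse Events).** The text says that "solicited symptoms of symptomatic influenza infection will be collected from the time of first exposure event through 7 days post-last-exposure", and that these are not AEs. Section 7.2 repeats this under Time Period and Frequency for Event Assessment and Follow-Up.
- **Antiviral rule (Section 7.2, same paragraph as the last-exposure rule).** "Events that occur after administration of antivirals will also be considered unsolicited AEs". It has no limit on severity, no exception for solicited symptoms, and no condition that the event be new or worse.

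Section 6.6 sets when an antiviral starts: "No later than 72 hours of a Recipient demonstrating any criteria which satisfy the primary outcome of SAR influenza infection", or sooner on certain clinical triggers. For a Recipient who consents to continue as a Donor it is withheld. That person may stop "before the maximum 5 days, as originally intended for a Donor participant", and an antiviral can then be given. Footnote 8 to the Recipient schedule in Appendix D makes the same exception.

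Section 7.1 makes the frequency and severity of non-serious AEs one of its safety measures and refers forward to Section 7.2 for the definition.

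**The concern.** Site staff apply the AE definition daily, and it decides what reaches the AE form. With two anchors and an unqualified antiviral clause, two clinicians can follow the text and classify the same mild cough differently. The difference is not random. It depends on when an antiviral was started and on whether the participant was a Recipient, a Donor, or a Recipient who became a Donor. A reported frequency of mild or moderate AEs would then partly reflect those circumstances rather than harm. Events coded inconsistently at entry are hard to recover in analysis.

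**Working it through.** The document states no AE or symptom rate, so there is no figure to reproduce. The check lays the three rules on one time scale.

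**Notation.** Day 0 is illness onset, L the day of last exposure, A the day of the antiviral.

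**Inputs**
- Donor onset is within 48 hours before entry to the exposure event (Section 3.2, inclusion criterion 5).
- Donor stay is 2 to 5 days (Section 6.9).
- The Donor phase of an infected Recipient is at most 5 days (Section 6.6).
- The antiviral starts 0 to 72 hours after a Recipient meets the outcome (Section 6.6).

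**Assumptions**
- Onset coincides with meeting the outcome criterion.
- A Recipient who does not become a Donor is last exposed 0 to 2 days before onset.
- A Donor's last exposure falls at the end of the stay.
- The antiviral rule applies from the day after the first dose.

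**Onset rule against last-exposure rule.** The first exemption ends on day 7, the second on day L + 7. They disagree on |L| days.

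- Donor, onset at entry, 2-day stay: L = 0 + 2 = 2. The windows end on days 7 and 9, a gap of 2 days.
- Donor, onset 48 hours before entry, 5-day stay: L = 2 + 5 = 7. The windows end on days 7 and 14, a gap of 7 days. Counted from entry, these are days 5 and 12.
- Recipient who then serves 5 days as a Donor: L = 5. The windows end on days 7 and 12, a gap of 5 days.
- Other infected Recipient: L = 0 to -2. The second window ends on day 7 down to day 5, a gap of 0 to 2 days.

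**Antiviral rule against onset rule.** The same finding is both exempt and an AE on days A + 1 to 7, which is 7 - A days.

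- Antiviral on day 0: days 1 to 7, 7 days.
- Antiviral at 72 hours (A = 3): days 4 to 7, 4 days.
- Antiviral after a 5-day Donor phase (A = 5): days 6 to 7, 2 days.
- No antiviral: 0 days.

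**Antiviral rule against last-exposure rule.** The overlap is L + 7 - A days. For an ordinary Recipient with A from 0 to 3 it runs from 7 days (L = 0, A = 0) to 2 days (L = -2, A = 3). For a Recipient who served 5 days as a Donor and was then treated it is 5 + 7 - 5 = 7 days. The antiviral clause therefore conflicts with both exemptions.

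**Laboratory findings.** Section 8.1.5 takes safety bloods, including lymphocyte count, 36 to 60 hours after virological confirmation, when an antiviral may already have started. Mild lymphopenia at that draw is exempt under Section 7.1 and an AE under the antiviral rule.

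**The case against.** **A default exists.** Section 7.2 asks that doubtful observations be reported. This does not reconcile the rules: the sentence sits under the assessment of causality, and applied here it would cancel both explicit exemptions.

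**The antiviral sentence may mean only new events or drug effects.** That is plausible, but it is not written. Nor can the sentence mean only events inconsistent with influenza, because the sentence before it already covers those.

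**Days are not events.** This stands. AEs are recorded with start and stop dates, and Section 7.2 combines clearly related findings into one diagnosis. A cough that began before the antiviral and continues has not plainly occurred after it. The overlap days show where the text contradicts itself; they are not a number of extra AEs.

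**The Donor gap of 7 days is a worst case.** This stands. It needs both the earliest onset and the longest stay, and the extra days fall after discharge, when daily symptom collection has ended.

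**The broad antiviral clause is conservative.** This stands in part. Section 2.5.1 lists headache, cough and fatigue among oseltamivir adverse events, so narrowing the clause has a price.

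The documents do not support three stronger readings that a reader might infer.

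- *A Recipient who becomes a Donor contributes no such AEs.* Section 6.6 allows an antiviral when the Donor phase ends, and the clause then applies.
- *About 44 Recipients are affected (0.25 × 175 = 43.75).* Section 2.3 ties 25% to low air hygiene, and 175 is a ceiling. If, for illustration, half were intervention Recipients with the 76% reduction assumed in Section 9.2, the figure would be 87.5 × 0.25 + 87.5 × 0.25 × 0.24 ≈ 27, before any effect of high air hygiene.
- *A planned safety comparison is biased.* The protocol plans no comparison of treated Recipients with Recipients turned Donor, and the antiviral rule does not depend on randomised group. The monthly review in Section 6.11 centres on severe or Grade 3 and higher events, which this does not touch.

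**Conclusion.** The point holds as an internal contradiction limited to mild or moderate influenza findings. The exemption windows differ by 2 to 7 days for Donors, 5 days for a Recipient who then serves 5 days as a Donor, and about 0 to 2 days for other infected Recipients. The antiviral clause overlaps the Section 7.1 exemption on 4 to 7 days with treatment at 0 to 72 hours, about 2 days after a 5-day Donor phase, and 0 days without treatment. These figures rest on the assumptions listed with the calculation, chiefly the timing of last exposure relative to onset.

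Because the frequency of non-serious AEs is a stated safety measure, the text is wrong as it stands, not merely short of detail. Its reach is modest. Severe symptoms, listed complications, serious AEs and the primary endpoint are unaffected, and the change in AE counts cannot be computed because no symptom or AE rates are given. It should be corrected.

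**What to change.** Reconcile three places so that they carry identical wording: Section 7.1, the definition paragraph of Section 7.2, and the repeat under Time Period and Frequency.

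1. Use one exemption window. For infected participants it runs from illness onset, which for Donors means onset before entry. Keep a stated exposure-based window for solicited symptoms in Recipients without confirmed infection, who have no illness onset to count from.
2. Limit the antiviral clause to events that are not on the solicited list, or that newly appear or worsen after the first dose. Listed symptoms already present and continuing are then not counted again as AEs.
3. Record the antiviral start date and tabulate events before and after it.

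The cost is edits to three paragraphs, the AE form instructions and, if not already collected, one date field. The downside is that a mild antiviral side effect that mimics a symptom already present, such as headache, cough or fatigue, stays in the solicited data; the before-and-after tabulation can still show it. The change concerns event classification only and leaves the timing of antivirals as it is.

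### The Related and Not Related definitions in section 7.2 overlap with no precedence rule, so the section 7.1 count of intervention-related SAEs is not reproducibly defined

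*Protocol*

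**What the plan says.** Protocol section 7.2, under Relationship to Study Intervention, sets a two-way label: "The relationship to study intervention must be assessed for AEs using the terms: related or not related".

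Related has three alternatives. The first is "The AE is known to occur with the study intervention". The second and third are that "there is a reasonable possibility that the study intervention caused the AE, or there is a temporal relationship between the study intervention and event".

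Not Related also has three. The first is "There is not a reasonable possibility that the administration of the study intervention caused the event". The second and third are that "there is no temporal relationship between the study intervention and event onset, or an alternate etiology has been established".

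The same paragraph explains reasonable possibility as evidence pointing towards causation. It gives no time window for a temporal relationship and no rule for an event that meets both definitions.

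The label feeds a safety measure. The first item in the section 7.1 list of what safety will be assessed by is "Study intervention-related serious adverse events occurring from the time of the first exposure event until 2 months post-discharge".

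**The concern.** A two-category scale works only if each event falls into exactly one category. Here a single criterion is enough on each side, and the criteria are not opposites of one another. Take a fracture from a witnessed fall two days after an exposure event. An assessor who looks at timing may call it Related, and one who looks at cause may call it Not Related. Both have followed the protocol.

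What is at stake is the numerator of the related-SAE measure. Recipients are healthy volunteers deliberately exposed to influenza with no direct benefit, so a reproducible count of attributable serious harm matters. The trial is open (section 6.1), so assessors who apply an indeterminate rule may know the assignment. The definitions are applied by site clinicians as events occur, and a later analysis plan could not restore consistent labels.

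**Working it through.** The plan states no figure to reproduce. The check is one of logic.

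**Inputs (section 7.2, Relationship to Study Intervention).** Four yes/no attributes of an event:
- K: known to occur with the study intervention
- R: reasonable possibility of causation
- T: temporal relationship
- A: alternate etiology established

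**Definitions as written.**
- Related = K or R or T
- Not Related = (not R) or (not T) or A

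**Enumeration.** Four attributes give 2 × 2 × 2 × 2 = 16 combinations.
- Related only requires R, T and not A, with K free: 2 combinations.
- Not Related only requires not K, not R and not T, with A free: 2 combinations.
- Neither: 0.
- Both: 16 − 2 − 2 − 0 = 12.

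| | Related only | Not Related only | Both | Neither |
|---|---|---|---|---|
| All 16 | 2 | 2 | 12 | 0 |
| T = yes (8) | 2 | 0 | 6 | 0 |
| T = no (8) | 0 | 2 | 6 | 0 |

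**The two overlaps that matter most, with T = yes.**
- T with A: 4 combinations (K and R free), all in both categories.
- T without R: 4 combinations (K and A free), all in both categories.
- The two sets share 2 combinations (not R with A), so together they make 4 + 4 − 2 = 6 of the 8.

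Some cells are clinically implausible, and the counts say nothing about how often each occurs.

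**Comparison with the rest of section 7.2.** The definition of an unanticipated problem explains possibly related by reasonable possibility alone, with no temporal alternative. The AE definition therefore applies a different standard from one the same section already uses, and its timing alternative bypasses the evidence requirement attached to reasonable possibility.

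**After the fix.** If Related = R and Not Related = not R, the 16 combinations split 8 and 8, with 0 in both and 0 in neither.

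**The case against.** The best defence is that causality is a matter of medical judgment (section 7.2, Classification of an Adverse Event). On that view a clinician would read temporal relationship as plausible timing and let an established other cause prevail. The SAE bullets in section 7.2 lend some support: they ask for an alternate etiology where the event is not related, which ties that criterion loosely to the Not Related branch. That is guidance, not a stated tie-break. It also leaves open the event with a temporal relationship, no reasonable possibility of causation and no identified other cause.

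A second defence is that little depends on the label, and most of this stands. Section 7.2 says relatedness does not decide what is reported and that AEs are documented whatever their relationship. SAE causality is assessed only by the site principal investigator or a co-investigator, and SAEs are then reviewed by sponsor medical staff and the IRB. A temporary halt under section 6.11 rests on judgment, not on a related-SAE count. The sample size and primary analysis (sections 9.2 and 9.3) do not use the label. One exception is that, after study completion, reporting an SAE to the IRB depends on its being suspected to be related.

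A third point is that removing timing as a sufficient criterion makes labelling less conservative in a deliberate-exposure study. That is a genuine cost, and the fix has to answer it.

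**Conclusion.** The point holds as a contradiction within a stated rule. The two categories are not mutually exclusive, no precedence is given, and the related-SAE count in section 7.1 is therefore not reproducibly defined. This rests only on reading 'or' in its ordinary sense. The number of SAEs affected cannot be stated, because the documents give no expected SAE count. The change should be made, but the primary result does not depend on it.

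A reader might go further and infer that every collected event is Related, since collection starts at exposure, and that the measure cannot discriminate at all. The documents do not support that. It would need temporal relationship to mean any onset after first exposure, and no window is stated. The Not Related alternative that "there is no temporal relationship between the study intervention and event onset" implies that some collected events lack one. It would also need study intervention to mean the exposure, yet section 6.1 describes Control Recipients as having no intervention. The recipient schedule in Appendix D also appears to mark AE reporting from admission, before exposure, although that table is broken in extraction. Finally, 6 of the 8 combinations with a temporal relationship also qualify as Not Related, so the label is indeterminate, not uniformly Related.

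**What to change.** Amend section 7.2 so that the categories are exclusive and exhaustive:
- Related: there is a reasonable possibility, as the section already explains that term, that the study intervention caused the event.
- Not Related: there is no such possibility.
- Known association, timing and alternate etiology are evidence to weigh in that judgment. None is a separate criterion, and timing alone does not decide the label.

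In the same place, state that study intervention for causality assessment covers the exposure events and study procedures in both arms. Without this, the label has no clear object for Control Recipients.

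The cost is a few sentences in section 7.2 and the matching eCRF help text. The small downside is that fewer events are labelled Related by default. To offset it, report all SAEs alongside the related ones in the section 7.1 summary. No event goes unrecorded, because recording does not depend on the label.
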